### 6.5 Withdrawal Criteria (if applicable)

If at any time during the study the investigator determines that a subject's safety has been compromised, the subject may be withdrawn from the study.

[figure not shown]
Subjects may withdraw consent from the study at any time.

Sponsor and/or investigator may discontinue any subject for non-compliance or any valid medical reason (see Section 9.6.2).

### 7 STUDY PARAMETERS

### 7.1 Efficacy Measures and Endpoints

### 7.1.1 Efficacy Measure(s)

### 7.1.2 Efficacy Endpoint(s)

The efficacy endpoints are changes from baseline at weeks 2, 4, 8 and 12 for each efficacy measure, where available. Endpoints will be calculated pre-CAE and, where available post-CAE and as pre- to post-CAE changes.

### 7.1.3 Criteria for Effectiveness

Success would be demonstrating statistically significant (p<0.05) effects on at least one DED sign or at least one DED symptom at week 12

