### 4 CLINICAL HYPOTHESES

The clinical hypotheses for this study are that 0.10% and/or 0.25% Reproxalap Ophthalmic Solution is superior to vehicle

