### 5 OVERALL STUDY DESIGN

This is a Phase 2b, multicenter, randomized, double—masked, vehicle-controlled, parallel-group design with block enrollment. Subjects will be randomized to one of the following treatment groups at Visit 2 and will be instructed to follow a QID-dosing regimen:

[figure not shown]
- Reproxalap 0.1% Ophthalmic Solution (N~100)
- Reproxalap 0.25% Ophthalmic Solution (N~100)
- Vehicle of Reproxalap Ophthalmic Solution (N~100)

[figure not shown]
This study is multicenter, randomized, double—masked, vehicle—controlled, parallel-group design with block enrollment. Approximately 300 subjects will be randomly assigned to one of the three treatment groups (1:1:1) to receive either Reproxalap Ophthalmic Solution (0.1%, 0.25%) or vehicle solution as topical ophthalmic drops administered bilaterally QID. Subjects, Sponsor, CRO and site personnel will be masked to treatment assignment.

During the screening period, two 90-minute exposures to the CAE® will be conducted to ascertain eligibility to enter the study. Those who qualify will be randomized to receive study drug in a double-masked fashion for 84 days. Subjects will self-administer drops four times daily and will complete daily diary assessments as instructed.

At Visit 6 (Day 85), CAE® exposure will occur, with pre-CAE®, during CAE® (symptoms only) and post-CAE® assessments of ocular signs and symptoms. At Visits 3, 4 and 5, no CAE® exposure will occur

The total number of expected participants, including screen failures, is approximately 750 subjects.

Subjects who terminate early during the treatment period will be asked to complete safety assessments prior to commencement of any alternative dry eye therapy (if at all possible). Subjects who are terminated early from the study will not be replaced.

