#### 11.4.1 General Considerations

Quantitative variables will be summarized descriptively using number of subjects (n), mean, standard deviation, median, minimum, and maximum. Qualitative variables will be summarized using counts and percentages.

All summaries will be presented by treatment group. Summaries will be provided for demographics, baseline medical history, concurrent therapies, and subject disposition.

For the purpose of summarization, medical history, concurrent therapies, and adverse events will be coded to MedDRA and WHO Drug dictionaries, as appropriate.

All analyses will be 2-sided at a significance level of 0.05. 80% and 95% confidence intervals will be provided where appropriate.

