#### 11.4.4 Multiplicity Consideration

As this is a Phase 2b study, there will be no multiplicity adjustments for the two active treatments or for the multiple endpoints.

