2.1 Study Variables

In this Phase 2b study there are no primary or secondary endpoints. All endpoints are considered hypothesis-generating and not hypothesis-testing. Efficacy variables and safety variables follow.

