8.5 Adjustments for Multiplicity

As this is a Phase 2b study, there will be no multiplicity adjustments for the two active treatments or for the multiple endpoints.

9. Disposition of Subjects

Subject disposition will be presented

10. Demographic and Pretreatment Variables

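### The protocol declares success if any one sign or symptom reaches unadjusted p<0.05 at week 12. That conflicts with the SAP's exploratory status, and the verdict does not carry the error rate of one test.

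*Protocol*

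**What the plan says.** Protocol 7.1.3, headed as the criteria for effectiveness, states: "Success would be demonstrating statistically significant (p<0.05) effects on at least one DED sign or at least one DED symptom at week 12". The visible sentence names no measure, dose, direction or CAE time point.

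Four other places determine how many chances the rule has:

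- **Doses.** The clinical hypothesis in Protocol 4 is that "0.10% and/or 0.25% Reproxalap Ophthalmic Solution is superior to vehicle", so a result on either dose can count.
- **Level of each test.** Protocol 11.4.1: "All analyses will be 2-sided at a significance level of 0.05".
- **Adjustment.** Protocol 11.4.4 says "there will be no multiplicity adjustments for the two active treatments or for the multiple endpoints", and SAP 8.5 repeats this.
- **Versions of each endpoint.** Protocol 7.1.2: "Endpoints will be calculated pre-CAE and, where available post-CAE and as pre- to post-CAE changes". Protocol 5 schedules a CAE exposure at Visit 6, so more than one version of a measure may exist at week 12.

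Against this, SAP 2.1 sets no endpoint hierarchy and says: "All endpoints are considered hypothesis-generating and not hypothesis-testing". SAP 2.4 and SAP 13 nevertheless say that hypotheses and endpoints are to be tested, and their visible text does not call those tests exploratory.

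**The concern.** A rule that returns success when any one of several p-values falls below 0.05 is a hypothesis test with a verdict. SAP 2.1 says the trial does no hypothesis testing. Both statements cannot describe the same endpoints, and no visible SAP text withdraws or relabels the protocol criterion.

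The absence of adjustment is not the objection. It is disclosed and is a normal choice for a trial meant to inform Phase 3. What is at stake is how the verdict will be read. Someone told that the trial met its criterion for effectiveness would attach the stated 0.05 to that statement, or 2.5% in the direction of benefit. That figure belongs to a single test, not to an any-one rule over several endpoints and two doses.

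**Working it through.** **What can be reproduced.** The only stated figure is the two-sided 0.05 per test. It is the error rate of one test: 1 − (1 − 0.05)^1 = 0.05, of which half, 0.025, lies in the direction of benefit. No familywise rate is visible to reproduce.

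**Inputs from the documents**
- Three arms, 1:1:1, about 100 per arm (Protocol 5).
- Two dose comparisons against the same vehicle arm. With equal arms, the two test statistics for one endpoint correlate at 0.5.
- A favourable hit is z > 1.96 at week 12. Weeks 2, 4 and 8 are not counted, because 7.1.3 names week 12 only.

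**Assumptions**
- *Number of week-12 endpoints, K.* The list is not visible. The SAP table list shows nine measure families: lissamine green staining, fluorescein staining, TFBUT, Schirmer's test, the Ocular Discomfort Scale, the Ocular Discomfort & 4-Symptom Questionnaire, OSDI, SANDE and tear osmolarity. K is taken as 1, 2, 5 and 9. K = 2 (one sign, one symptom) is the smallest reading of the rule's wording. Some families may have no week-12 test, while sub-scores and CAE versions could add more.
- *Correlation between endpoints, ρ.* Not given; equal correlations from 0 to 0.9 are used.

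**Method.** Quantity computed: P(at least one of the 2K statistics exceeds 1.96) when neither dose has any effect. It was simulated with 200,000 to 400,000 runs per case.

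| Endpoints × doses | ρ = 0 | 0.3 | 0.5 | 0.7 | 0.9 |
|---|---|---|---|---|---|
| 1 × 2 (2 tests) | 4.5% | 4.5% | 4.5% | 4.5% | 4.5% |
| 2 × 2 (4 tests) | 8.9% | 8.5% | 8.1% | 7.4% | 6.3% |
| 5 × 2 (10 tests) | 20.7% | 18.1% | 15.7% | 12.8% | 9.0% |
| 9 × 2 (18 tests) | 34.1% | 27.5% | 22.5% | 17.1% | 10.7% |

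The comparator in every cell is 2.5%. The first row needs no assumption about correlation between endpoints.

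**Check against a closed form.** If all tests were independent, the rate would be 1 − 0.975^m: 4.9% for m = 2, 9.6% for m = 4 and 36.6% for m = 18. The simulated values at ρ = 0 lie slightly below these, as the shared vehicle arm implies.

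**If either direction counted.** The visible 7.1.3 does not name a direction. Against 5% for one test, the rates would be 9.0% (2 tests), 12.6% to 17.3% (4 tests) and 21.4% to 57.5% (18 tests).

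**What a changed significance level would have to be.** To bring the benefit-direction rate to 2.5%, the critical value would have to be:
- 4 tests: 2.478 at ρ = 0 and 2.353 at ρ = 0.9, equivalent to two-sided levels of 0.0132 and 0.0186;
- 18 tests: 2.979 and 2.607, equivalent to 0.0029 and 0.0091.

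**The case against.** The strongest reply is that much of the relevant text cannot be seen. The visible sentences in Protocol 4 and 7.1.3 and in SAP 2.4 may be cut. Protocol 11.2 and 11.3 appear in the contents but show no text, Protocol 11.4.5 is an empty heading, and the SAP 2.2 list is not visible. Those sections might say which comparisons count. SAP 1 also states that its statistical methods replace the protocol's, and SAP 17 has an entry on the significance level whose content is redacted. On that reading SAP 2.1 may already supply the exploratory status, and 0.05 may not be the operative level.

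This limits certainty but does not remove the point. The precedence clause covers analysis methods; whether it reaches a success criterion in the protocol's study-parameters section is arguable. A changed level would restore 2.5% only if it were about as strict as the values worked out above, and it would still leave a success verdict beside SAP 2.1.

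A second reply is that the harm is inferred. Both documents disclose the lack of adjustment, and no visible text ties a decision to success. That is fair, and it is why this is a wording correction rather than a design fault. The disclosure still does not tell a reader what error rate the verdict carries.

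A third reply is that the rates are scenarios, not estimates. That also stands: the 18-test row should not be quoted as the trial's error rate. The conclusion does not need it, because the two-test case already nearly doubles 2.5%. That case does rely on either dose counting, as Protocol 4 visibly says.

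**Conclusion.** The concern holds on the visible text. Protocol 7.1.3 gives a pass/fail verdict that SAP 2.1 says the trial does not make, and nothing visible reconciles them.

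An ineffective drug would meet the rule in its own favour 4.5% of the time on one endpoint with two doses, 6% to 9% of the time on the smallest reading of the rule, and 11% to 34% of the time if all nine measure families have one week-12 test per dose. At correlations of 0.3 to 0.7 the last range is 17% to 28%. The excess over 2.5% rests on two dose comparisons each at 0.05; its exact size rests on the assumed test count and correlations.

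Confidence is moderate because of the redactions. It should be fixed, since it affects what the trial may be said to have shown.

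**What to change.** First check the unredacted Protocol 4, 7.1.3 and 11.2 and SAP 2.4 and 17. If they do not resolve the conflict:

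1. Relabel the 7.1.3 sentence as a descriptive, non-confirmatory signal for choosing Phase 3 endpoints, or delete it.
2. State in SAP 2.4 and 13 that the tests are nominal and exploratory, in line with SAP 2.1.

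This needs wording in two documents, no patients and no power. The sponsor gives up a success claim. The Phase 3 objective in Protocol 3 rests on effect sizes and loses nothing.

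Only if a success claim is kept: before unmasking, fix the set of week-12 dose-by-endpoint comparisons, including which sub-scores and CAE versions count. Base the claim on a multiplicity-adjusted p-value in the direction of benefit, for example permutation max-T, which respects the correlations. Keep nominal p-values and confidence intervals as descriptive.

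That option costs power. For an assumed standardised difference of 0.4 and 100 per arm, the non-centrality is 0.4 × √(100/2) = 2.83. Power for one comparison is Φ(2.83 − critical value): 81% at 1.96, 64% to 68% for 4 tests and 44% to 59% for 18 tests (ρ from 0 to 0.9).

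Do not replace the rule with a count of nominal hits judged against 0.025 × the number of tests. With 18 tests the expected count under no effect is 0.45 at any correlation, but the chance of five or more hits rises from 0.03% at ρ = 0 to 3.9% at ρ = 0.9.

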### 7.2 Safety Measures

- Visual acuity (ETDRS);
- Slit-lamp biomicroscopy;
- Adverse event query;
- Dilated Fundoscopy;
- Intraocular Pressure;

### 8 STUDY MATERIALS

### 8.1 Study Treatment(s)

- 8.1.1 Study Treatment(s)/ Formulation(s)
  - Reproxalap Ophthalmic Solution (0.25%)
  - Reproxalap Ophthalmic Solution (0.10%)
  - Vehicle Ophthalmic Solution
- 8.1.2 Description of and Justification for the Route of Administration, Dosage, Dosage Regimen, and Treatment Period(s).

Topical ophthalmic dosing is the optimal route of administration for dry eye treatments. The dosage and dosage regimen was selected based on nonclinical and clinical studies described in Section 2.

8.1.3 Instructions for Use and Administration

### 9 STUDY METHODS AND PROCEDURES

### 9.1 Subject Entry Procedures

### 9.1.1 Overview

Subjects as defined by the criteria in sections 6.2, 6.3, and 6.4 will be considered for entry into this study.

### 9.1.2 Informed Consent

Prior to a subject's participation in the trial (i.e., changes in a subject's medical treatment and/or study related procedures), the study will be discussed with each subject, and subjects wishing to participate must give written informed consent using an informed consent form. The informed consent form must be the most recent version that has received approval/favorable review by a properly constituted Institutional Review Board (IRB).

### 9.1.3 Washout Intervals

Prohibited medications, treatments, and activities are outlined in the exclusion criteria (Section 6.4).

### 9.1.4 Procedures for Final Study Entry

Subjects must meet all inclusion and none of the exclusion criteria.

### 9.1.5 Methods for Assignment to Treatment Groups:

Before the initiation of study run-in at Visit 1, each subject who provides written and informed consent will be assigned to a screening number. All screening numbers will be assingned in strict numerical sequence at a site and no numbers will skipped or omitted. Each subject who meets all the inclusion and none of the exclusion criteria at Visit 1 and Visit 2 will be assigned a randomization number at the end of Visit 2. The Interactive Web Response System (IWRS) will be used to assign all randomization numbers.

Randomization and kit numbers will be assigned automatically to each subject as they are entered into the IWRS.

The site staff will dispense kit(s) required until the next visit. Both the randomization number and the dispensed study drug kit number(s) will be recorded on the subject's

source document and eCRF. The sponsor, investigators, and study staff will be masked during the randomization process and throughout the study.

### 9.2 Concurrent Therapies

The use of any concurrent medication, prescription or over-the-counter, is to be recorded on the subject's source document and corresponding electronic case report form (eCRF) along with the reason the medication was taken.

Concurrent enrollment in another investigational drug or medical device study is not permitted.

### 9.2.1 Prohibited Medications/Treatments

Disallowed medications/treatments during the study are outlined in the Exclusion Criteria (Section 6.4).

### 9.2.2 Escape Medications

No escape medications are required for this study.

### 9.2.3 Special Diet or Activities

No special diets or activities are required for this study.

### 9.3 Examination Procedures

# 9.3.1 Procedures to be Performed at Each Study Visit with Regard to Study Objective(s)

Procedures listed below should be performed in the given order. See Appendix 2 for details on methodologies and grading systems.

### 9.3.2 Visit 1: Day $-14 \pm 2 - CAE^{\circ}$ Screening

All subjects will undergo the following screening assessments:

- Demographic Data and Medical/Medication/Ocular History
- Review of Inclusion/Exclusion Criteria
- Urine Pregnancy Test (for females of childbearing potential): Women of childbearing potential must have a negative urine pregnancy test to continue in the study

Post−CAE®

- AE Query
- IOP
- Dilated Fundoscopy
- Review of Inclusion/Exclusion Criteria
- Run-in Instillation at the Study Site: All subjects having a positive response (as
  defined above) and meeting all other screening eligibility criteria at the end of Visit 1
  will receive run-in drops for dosing. Qualified subjects will self-administer their
  initial run-in dose bilaterally at the study site under supervision of a trained
  technician.
- Run-in (Vehicle) and Diary Dispensation: Prior to discharge from the study site on
  Day -14, subjects will be dispensed sufficient Run-in supply to last until Visit 2 and
  will be educated in diary recording and self-administration of vehicle run-in. Subjects
  will be instructed to self-administer one drop QID in each eye until Visit 2. Subjects
  will be instructed NOT to instill run-in on the morning of their next scheduled study
  visit (Visit 2).

- AE Query
- Subjects will be scheduled for Visit 2.

- Diary/Run-in Collection
- Review of Inclusion/Exclusion Criteria
- Medical/medication history update
- AE query

[figure not shown]

- Review of Inclusion/Exclusion Criteria
- Randomization
- Study Drug Instillation at the Study Site: All subjects having a positive response (as
  defined above) and meeting all other screening eligibility criteria at the end of Visit 2
  will be randomized to one of three treatment groups utilizing the IWRS system.
  Randomized subjects will self-administer their initial study drug dose bilaterally at
  the study site under supervision of a trained technician.
- Study Drug Diary/Study Drug Dispensation: Prior to discharge from the study site on Visit 2 (Day 1), randomized subjects will be educated in study drug diary recording and self-administration of study drug. Subjects will receive their assigned study drug kit with sufficient supply to last until Visit 3 and will be instructed NOT to selfadminister study drug on the morning of their next scheduled study visit (Visit 3).
- AE Query
- Subjects will be scheduled for Visit 3.

### 9.3.4 Visit 3 (Day 15 ±2)

- Study Drug Diary/Study Drug Collection
- Medical/medication history update
- AE query

Study Drug Diary/Study Drug Dispensation: Prior to discharge from the study site on
Visit 3, subjects will be assigned a new study drug kit via the IWRS and will also be
re-dispensed the remaining unused ampules from their previous kit for at-home
dosing up to Visit 4. Subjects will again be educated in study drug diary recording
and self-administration of study drug. Subjects will be instructed to NOT selfadminister study drug on the morning of their next scheduled study visit (Visit 4)

- AE Query
- Subjects will be scheduled for Visit 4.

### 9.3.5 Visit 4: Day $29 \pm 2$

- Study Drug Diary/Study Drug Collection
- Medical/medication history update;
- AE query;

- Study Drug Diary/Study Drug Re-dispensation: Prior to discharge from the study site
  on Visit 4, subjects will be assigned two new study drug kits via the IWRS and will
  also be re-dispensed the remaining unused ampules from their previous kits for athome dosing up to Visit 5. Subjects will again be educated in study drug diary
  recording and self-administration of study drug. Subjects will be instructed to NOT
  self-administer study drug on the morning of their next scheduled study visit (Visit 5)
- AE Query
- Subjects will be scheduled for Visit 5.

### 9.3.6 Visit 5: Day $57 \pm 3$

- Study Drug Diary/Study Drug Collection
- Medical/medication history update
- AE query

•

- Study Drug Diary/Study Drug Re-dispensation: Prior to discharge from the study site
  on Visit 5, subjects will be assigned a new study drug kit via the IWRS and will also
  be re-dispensed the remaining unused ampules from their previous kits for at-home
  dosing up to Visit 6. Subjects will again be educated in study drug diary recording
  and self-administration of study drug. Subjects will be instructed to NOT selfadminister study drug on the morning of their next scheduled study visit (Visit 6)
- AE Query
- Subjects will be scheduled for Visit 6.

### 9.3.7 Visit 6: Day $85 \pm 3$

[figure not shown]

- Drug Diary/Study Drug Collection
- · Medical/medication history update
- AE query
- Urine Pregnancy Test (for females of childbearing potential)
- · \_\_\_\_\_

- .
- Utilizing an ETDRS Chart

- Intraocular Pressure
- Dilated fundoscopy
- AE Query
- Study Exit

### 9.4 Schedule of Visits, Measurements and Dosing

### 9.4.1 Scheduled Visits

Refer to Appendix 1 for a schedule of visits and measurements.

### 9.4.2 Unscheduled Visits

These visits may be performed in order to ensure subject safety. All procedures performed at an unscheduled visit will be recorded in the source documents and on the Unscheduled Visit eCRF pages. Any procedure indicated in the eCRF that is not performed should be indicated as "Not done."

Evaluations that may be conducted at an Unscheduled Visit include:

- Slit-lamp Biomicroscopy
- Visual Acuity
- Intraocular Pressure
- Urine Pregnancy Test
- Dilated Fundoscopy
- Assessment of Adverse Events

- Assessment of concomitant medications and/or treatments
- Any other assessments needed in the judgment of the investigator.

### 9.5 Compliance with Protocol

Subjects will be instructed on proper use of the subject daily diary and proper instillation and storage of study drug at the end of Visits 1, 2, 3, 4 and 5, and given written

### 9.6 Subject Disposition

### 9.6.1 Completed Subjects

A completed subject is one who has not been discontinued from the study.

### 9.6.2 Discontinued Subjects

Subjects may be discontinued prior to their completion of the study due to:

- subject request/withdrawal
- AEs
- protocol violations
- administrative reasons (e.g., inability to continue, lost to follow up)
- sponsor termination of study
- other

Note: In addition, any subject may be discontinued for any sound medical reason.

Notification of a subject discontinuation and the reason for discontinuation will be made to Ora and/or sponsor and will be clearly documented on the eCRF.

### 9.7 Study Termination

The study may be stopped at any time by the investigator, the sponsor, and/or Ora with appropriate notification.

### 9.8 Study Duration

An individual subject's participation will involve 6 visits over approximately a 14-week (~98 days) period (84 days of treatment and 14 days pre-screening).

### 9.9 Monitoring and Quality Assurance

During the course of the study an Ora monitor, or designee, will make routine site visits to review protocol compliance, assess IP accountability, and ensure the study is being conducted according to the pertinent regulatory requirements. The review of the subjects' medical records will be performed in a manner that adequately maintains subject confidentiality. Further details of the study monitoring will be outlined in a monitoring plan.

Regulatory authorities of domestic and foreign agencies, quality assurance and or its designees may carry out on-site inspections and/or audits which may include source data checks. Therefore direct access to the original source data will be required for inspections and/or audits. All inspections and audits will be carried out giving consideration to data protection as well as subject confidentiality to the extent that local, state, and federal laws apply.

